6.5 Additional Safety Assessments

6.5.1 Adverse Events

The applicable definition of an Adverse Event (AE) can be found in the study protocol Section 13 Device Deficiencies and Adverse Events. All AEs occurring from when a subject signs informed consent to when a subject exits the study will be accounted for in the reporting. Timing of the adverse event is specified by the investigator on the case report

form when the “Description of Adverse Event” category is selected. *Systemic* adverse events include non-ocular events and events in the fellow eye.

An overall summary of treatment emergent adverse events will be provided including the number and percentage of unique subjects/eyes with at least one AE, AE in the study eye, serious AE in the study eye, systemic AE, serious systemic AE, device related AE (ADE), serious device related AE (SADE), and AE leading to withdrawal.

Descriptive summaries (subject counts and percentages, event counts) for AEs will be presented by primary SOC and PT of the Medical Dictionary for Regulatory Activities (MedDRA) dictionary (Version 19.0 or a more recent version). The SOCs will be presented in alphabetical order. PTs will be ordered in decreasing proportion. The following summary tables and corresponding subject listings will be provided:

- ≠ Non-serious AEs in the study eye (TEAE only)
- ≠ Serious AEs in the study eye (TEAE only)
- ≠ Non-serious systemic AEs for all enrolled subjects (includes non-ocular events and events in the fellow eye)
- ≠ Serious systemic AEs for all enrolled subjects (includes non-ocular events and events in the fellow eye)
- ≠ Adverse device effects (ADE) for all study eyes(TEAE only)
- ≠ Serious adverse device effects (SADE) for all study (TEAE only)
- ≠ All adverse events occurring in the study eye prior to surgery

Both subject and event counts will be presented for AEs. Subject counts refer to the number of subjects with the respective AE of interest. Subjects who experience multiple AEs for a PT will be counted once, similarly for subjects with multiple AEs per SOC, for subject counts. Event counts refer to the number of occurrences of the respective AE of interest, regardless of whether a subject already had this event.

Additionally, individual subject listings provided will include:

- ≠ Deaths for all enrolled subjects
- ≠ Withdrawals due to AE(s) for all enrolled subjects

All reported adverse events will be detailed in the data listings. These listings will also include AEs, where appropriate, that occur after signing the ICF but prior to surgery.

6.5.2 Device Deficiencies

The applicable definition of a device deficiency is found in the study protocol Section 13.1.4. A listing of all device deficiencies, as recorded on the Device Deficiency CRF, will be provided.

6.5.3 Endothelial Cell Count

Endothelial cell count at baseline and at each follow-up visit at which the specular microscopy exam is conducted, will be summarized. In addition, change and percentage change from baseline as well as change between two consecutive visits will also be summarized.

6.5.4 Gonioscopy and Slit Lamp Findings

Gonioscopy and slit lamp results at baseline and at each follow-up visit at which the exams are conducted will be summarized by the number of abnormal findings in each category (numerator), the number of observations with data (denominator). A listing will be provided which presents all subjects with any abnormal slit lamp findings.

6.5.5 Fundus Examination

Fundus examination observations at baseline and at each follow-up visit at which the exams are conducted will be summarized by the number of abnormal findings in each category (numerator), the number of subject in the ITT cohort (denominator), and the percentage of abnormal findings in each category (numerator / denominator). Also, C/D ratio results will be summarized at each assessment visit for non-missing records. A listing will be provided which presents all subjects with any abnormal fundus exam observations. An additional listing will present the C/D ratio exam results.

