15.4.2.2 Analysis Methods

Continuous endpoints will be summarized by number of observations (n), mean, median, standard deviation, minimum and maximum; binary endpoints will be summarized by numerator (number of eyes meeting the endpoint), denominator, and the proportion of ITT eyes meeting the endpoint. Denominators for adverse events, slit lamp findings, and other events will be the number of eyes in the ITT set. Denominators for data such as visual acuity and other subject data that is collected at protocol-required visits will reflect the number of eyes with non-missing data in the ITT set. Summary statistics will be presented at all postoperative visits for which the endpoint data are collected. Supportive analysis will be conducted using the DI analysis set for all secondary effectiveness outcomes.

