15.5.4 Ocular Adverse Events

The number of events, number of eyes experiencing the event, and the rate of the event will be reported for all postoperative ocular adverse events occurring in study eyes. Any ocular events occurring pre-operatively in study eyes will be listed separately. Any ocular events occurring in non-study eyes will also be listed separately.

15.5.5 **Non-Ocular Adverse Events**

The number of events, number of subjects experiencing the event, and the rate of the event will be reported for all non-ocular adverse events.

15.5.6 **Device Deficiencies**

The number of device deficiencies by type will be calculated, and a listing of all device deficiencies will be provided.

15.5.7 **Endothelial Cell Count**

Specular microscopy data at baseline and at each follow-up visit at which the exam is conducted will be summarized with number of observation (n), mean, median, standard deviation, minimum, and maximum. Change and percentage change from baseline as well as change between two consecutive visits will also be summarized with number of observations (n), mean, median, standard deviation, minimum, and maximum.

15.5.8 **Slit Lamp and Fundus Examinations**

Slit lamp and fundus examination results at baseline and at each follow-up visit at which the exams are conducted will be summarized by the number of subjects in each category (numerator), the number of subjects with data (denominator), and the percentage of subjects in each category (numerator / denominator).

15.5.9 **Corneal Pachymetry**

Corneal pachymetry data recorded at screening and at each follow-up visit at which the exam is conducted will be summarized descriptively with number of observations (n), mean, median, standard deviation, minimum, and maximum.

15.5.10 **Visual Field Loss Mean Deviation Testing**

The visual field mean deviation testing data collected at baseline and at each follow-up visit at which the exam is conducted will be summarized with number of observations (n), mean, standard deviation, minimum, and maximum.

15.5.11 **Manifest Refraction**

The number of observations (n), mean, median, standard deviation, minimum, and maximum for sphere, cylinder, and manifest refraction spherical equivalent will be reported at baseline and at each follow-up visit for which manifest refraction is scheduled.

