2.1 Intention to Treat Analysis Set

The intention to treat (ITT) analysis set will be defined as the set of study eyes for which a CyPass Micro-Stent implant is attempted. The ITT analysis set will serve as the primary set for the safety and effectiveness summaries and analyses, as well as for all demographics, baseline, surgery, and study conduct summaries.

3 General Reporting Conventions

- ≠ All study eyes will receive the same treatment consisting of CyPass Micro-Stent implantation following uncomplicated cataract surgery. Therefore, summary tables will be presented for all subjects combined across all investigative centers.
- ≠ Available data at each assessment time point will be presented. No imputations will be made for missing data.
- ≠ Appropriate descriptive statistics will be computed and displayed (by assessment time point and other key variables as appropriate for both continuous and categorical variables as described below).

For continuous variables, descriptive statistics include n (number of subjects/eyes) with non-missing data, mean, standard deviation (SD), median, minimum and maximum values. The following number of decimal places will be used: mean and

median values to one more decimal place than the raw data; minimum, and maximum to the same number of decimal places as the raw data and SD to two more decimal places than the raw data.

For categorical parameters, the number and percentage of subjects/eyes within each category will be presented. The denominator for percentages will be based on the number of subjects/eyes with non-missing data appropriate for summary purposes. If a count of zero is obtained for categorical data, the zero count and percentage will still be displayed. Unless otherwise noted, percentages will be presented to one decimal place.

With the exception of the primary study endpoint, that is a one-sided test ($\alpha=0.05$), all other applicable confidence intervals (CI) will be at the $\alpha = 0.05$ (two-sided) level.

- ≠ Baseline is defined as the last assessments obtained prior to CyPass implantation surgery on Day 0.
- ≠ Change from baseline (pre-surgery) (where relevant) will only be summarized for subjects with both screening (pre-surgery) and post-op data for the relevant visit

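### SAP 6.5.5 divides fundus findings at each visit by the full ITT cohort, against protocol 15.5.8, so late-visit percentages are diluted by the fraction of eyes not examined

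*SAP*

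**What the plan says.** **SAP 6.5.5 (Fundus Examination).** Fundus observations are tabulated at baseline and at every follow-up visit with the examination. The numerator is the count of abnormal findings in a category. The denominator is "the number of subject in the ITT cohort (denominator"). The same section then treats the cup-to-disc ratio differently: "C/D ratio results will be summarized at each assessment visit for non-missing records".

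**Protocol 15.5.8 (Slit Lamp and Fundus Examinations).** The numerator is subjects in each category and the denominator is "the number of subjects with data (denominator").

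**SAP section 3 (General Reporting Conventions).** For categorical data: "The denominator for percentages will be based on the number of subjects/eyes with non-missing data appropriate for summary purposes". The same section adds: "No imputations will be made for missing data".

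**SAP 6.5.4 (Gonioscopy and Slit Lamp Findings).** The denominator is "the number of observations with data (denominator").

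**Protocol 15.4.2.2 (secondary effectiveness methods).** This section has two rules. One is "Denominators for adverse events, slit lamp findings, and other events will be the number of eyes in the ITT set". The other covers visual acuity and other data collected at required visits, whose denominators "will reflect the number of eyes with non-missing data in the ITT set".

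**The concern.** The SAP presents itself as carrying out protocol section 15, yet for this table it swaps the protocol's denominator for a larger one and gives no reason. In a table by visit, the full cohort suits the data only while everyone is examined. Once eyes are missing, and nothing is imputed, each missing eye lowers the percentage whatever its condition.

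Three things are at stake:

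- Percentages at later visits are pulled down, which is the unhelpful direction for safety data in a post-approval study.
- Because losses accumulate, a constant rate among examined eyes would print as a falling one.
- The fundus and slit lamp tables, which protocol 15.5.8 covers with one rule, would have different denominators at the same visit.

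The numerators differ as well. The protocol counts subjects and the SAP counts findings. If an eye can contribute more than one finding to a category, findings divided by subjects is not a proportion of eyes.

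**Working it through.** **Inputs**

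- Planned implanted eyes: 450 (protocol 15.8; SAP section 7).
- Planned eyes with 36-month follow-up: at least 360, allowing for up to 20% loss (same sections).
- ITT set: study eyes with an attempted implant (SAP 2.1), taken here as 450.
- Imputation: none (SAP section 3).
- Fundus examinations: screening and Visits 4 to 8 (schedule of visits).

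**Step 1. Reproduce the plan's figure.** 360 / (1 − 0.20) = 450. This matches both documents.

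**Step 2. Effect of the denominator.** Let A be the numerator count, N the ITT size and m the fraction of ITT eyes without a fundus examination at the visit.

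- SAP 6.5.5: A / N
- Protocol 15.5.8: A / [N(1 − m)]
- Ratio of the first to the second: 1 − m

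The relative shortfall is therefore m. It does not depend on A, so it is the same whether A counts findings or eyes.

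**Step 3. Month 36 at the planned maximum loss.** m = 0.20, and the ratio is 360/450 = 0.80.

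| Abnormal eyes (illustrative) | Divided by 360 | Divided by 450 | Relative shortfall |
|---|---|---|---|
| 9 | 2.5% | 2.0% | 20% |
| 18 | 5.0% | 4.0% | 20% |
| 36 | 10.0% | 8.0% | 20% |

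**Step 4. Range over assumed missingness, with 10% abnormal among examined eyes.** The documents give a loss figure for Month 36 only, so the other rows are assumptions.

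| Fraction missing | Eyes examined | Printed on the ITT denominator |
|---|---|---|
| 5% | 427.5 | 9.5% |
| 10% | 405 | 9.0% |
| 15% | 382.5 | 8.5% |
| 20% | 360 | 8.0% |
| 25% | 337.5 | 7.5% |

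Read downwards, the table also shows the effect on trend. If 5% were missing at an early visit and 20% at Month 36, a constant 10% would print as 9.5% and then 8.0%.

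**The case against.** The case for leaving the text alone has several parts.

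*An ITT denominator is not peculiar to this section.* A reader might infer that SAP 6.5.5 is the only place where it appears. It is not. SAP 5.1.2 divides unmedicated eyes with IOP in range at a postoperative visit by the ITT set, SAP 6.4 does so for IOP rises and acuity loss, and SAP 6.2 and 6.3 do so for event rates. What stands is narrower: among the visit-by-visit examination summaries in SAP 6.5, only the fundus section names the ITT cohort.

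*The protocol is not uniform.* Section 15.4.2.2 gives slit lamp findings and other events an ITT denominator, although 15.5.8 gives slit lamp results subjects with data. This is fair, but 15.4.2.2 does not name fundus findings, its next sentence uses non-missing data for visit-collected data, and 15.5.8 is the specific rule.

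*A specific section may override a general convention.* This also stands. SAP section 3 is qualified by what suits the summary, so 6.5.5 is out of line with it but does not flatly contradict it. The firm conflict is with protocol 15.5.8.

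*No eye is declared normal.* A reader might infer that unexamined eyes are reported as having a normal fundus. SAP 6.5.5 tabulates abnormal findings only, specifies no count of normal eyes, and nothing is imputed. The effect is dilution of the percentage.

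*The 20% may not be reached.* It is a planning maximum. Protocol 12.4 asks that subjects leaving early return for all Visit 8 procedures, which include the fundus examination. The SAP does not say whether those examinations are tabulated at Visit 8. If they are, fewer eyes are missing and the shortfall is smaller.

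*The harm is limited.* The numerator is shown, all subjects with abnormal fundus observations are listed, an accountability table is planned (SAP 4.1), and retinal detachment and severe choroidal events are counted separately as adverse events (SAP 6.3). This is why the point is minor.

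**Conclusion.** The point holds as a minor but real discrepancy. SAP 6.5.5 departs from protocol 15.5.8 and understates the percentage among examined eyes by the fraction not examined.

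At Month 36 the understatement is up to about 20% in relative terms, or 2.0 percentage points in the 10% example. That assumes an ITT set of 450, attrition at the planned maximum, and fundus data on exactly the 360 eyes that remain. It is smaller at earlier visits and near zero at baseline.

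It would go too far to state that Month 36 percentages will be 20% too low, or that a false decline will appear. Both depend on missingness that the documents only plan for. Nor does dividing by examined eyes remove bias if eyes that miss the visit differ from those seen; it gives a percentage with a clear meaning and a visible base.

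The summary is descriptive, with no hypothesis attached. The primary test, its denominator and the sample size are unaffected.

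**What to change.** Before database lock:

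1. In SAP 6.5.5, make the denominator the number of study eyes with a fundus examination at that visit, and print that n in each column.
2. In the same section, count eyes (subjects) in each category instead of findings, as protocol 15.5.8 does.
3. Align the matching numerator wording in SAP 6.5.4, so that the fundus, slit lamp and gonioscopy tables count the same unit.

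The cost is a few phrases in two adjacent SAP sections and the corresponding table programming. No new data are needed.

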6.5.6 Corneal Pachymetry

Central corneal thickness will be summarized at screening, 12, 24, and 36 months postoperatively. This will be measured three times for each subject for each visit, and the median value will be used to calculate summary statistics.

6.5.7 Intraocular Pressure

Descriptive summaries of observed intraocular pressure (IOP) values, as well as change and percent change from baseline values will be presented at each postoperative assessment visit. Subject listings of all IOP measurements along with the number of IOP medications will be presented by visit. IOP is measured twice within the eye. If the values are within 2 mmHg then the average is calculated, otherwise a third measurement is taken and the median of the three is used to represent the IOP at that visit for that eye.

6.5.8 Visual Field Loss Mean Deviation Testing

The visual field mean deviation (dB) testing data collected at screening, 12, 24, and 36 months postoperatively will be summarized. Also, a categorical summary of changes from screening will be presented using the following three categories: Increase (≥ 2.5 dB), No Change ($-2.5 < \text{dB} < 2.5$ dB), or Decrease (≤ -2.5 dB).

6.5.9 Manifest Refraction

Sphere, cylinder, and MRSE will be summarized at baseline and at each postoperative visit for which manifest refraction is scheduled.

All manifest refraction results (i.e., sphere (diopters), cylinder (diopters), and axis (degrees)) will be included in the data listings. Note, for cylindrical correction results (i.e., cylinder and axis) recorded in minus-cylinder notation will be converted to plus-cylinder notation for consistency in reporting. Details for this conversion can be found in Appendix D: Cylinder Adjustment Converting Negative to Positive Notation

6.5.10 Best Corrected Visual Acuity (BCDVA)

BCDVA (collected in letters read) will be summarized at baseline and at each post-operative visit at which BCDVA is collected; change from baseline will also be collected at each post-operative visit at which BCDVA is collected. A listing of BCDVA will also be provided. An additional listing of any instances where a loss of BCDVA of two lines or more is reported will also be provided. Data will be collected based on the visual acuity score (letters read). These values will be converted to and reported as Snellen values. Details for this conversion can be found in Appendix E: Conversion of Visual Acuity Score to Snellen Values

6.5.11 CyPass Explantation and/or Repositioning

A listing detailing subjects with CyPass explantation and/or repositioning will be provided. The listing will include the following variables: site-subject, age, sex, race, ethnicity, explantation or repositioning event, surgery date, study day, and reason. The data for this listing will be collected on the adverse events eCRF. Further details can be found in Appendix C: Data Sources.

7 Sample Size and Power Calculations

The performance target for the primary safety endpoint is 7.0%.

An evaluation of COMPASS (TMI-09-01) data showed that through 24 months of follow-up, there were two eyes with failures to implant and eight eyes with CyPass malposition events, respectively, corresponding to the above definitions. In addition, there were four eyes with documentation of three rings visible within the first postoperative week that likely would have undergone early secondary surgical intervention due to anterior CyPass positioning under the approach documented in the Instructions for Use (IFU). Inclusion of these cases would increase the number of observed events from 10 to 14 (3.74%, 95% confidence

interval: 2.1% – 6.2%). Of note, not all investigators documented the number of rings visible in the early postoperative period because this was not a study requirement (data regarding the number of rings is recorded for only 96 subjects at 1 Day and 139 subjects at 1 Week), so this number likely underestimates the number of subjects who would have been candidates for early surgical re-intervention under the new criteria described in the IFU.

Based on these considerations, the “true” event rate is assumed to be 4.0%, and the performance target is set to 7.0%. The following assumptions were used for the sample size calculation:

- ≠ Type I error = 0.05
- ≠ one-sided alternative

With a sample size of 360 subjects in the final analysis (unilateral implants only) and a performance target of 7.0%, assuming a true event rate of 4.0%, there is 80% power to reject the null hypothesis based on a one-sided alpha = 0.05-level exact test for a single proportion.

To allow for attrition over this 36-month study, a cumulative rate of up to 20% of subjects lost to follow-up is assumed, corresponding to a targeted implantation of 450 eyes in 450 subjects to achieve at least 360 eyes with 36 months of follow-up.

Annex F of ANSI standard Z80.27-2014 refers to ensuring adequate sample size so that any adverse event of a given type that occurs in the population at a rate of 1% or greater is likely to be seen in the study. With 360 subjects, there is at least 97% probability that at least one adverse event will be detected, assuming a true rate of 1.0%. There is at least 95% probability if the true rate is 0.83%.

8 References

American National Standards Institute, Inc. ANSI Z80.27-2014

COMPASS (TMI-09-01) trial CSR.

9 Revision History

This is the original (Version 1.0) Statistical Analysis Plan for this study. This version of the Statistical Analysis Plan is based on the version of the study protocol with effective date 22-Aug-2017.

10 Appendix A: Schedule of Visits

Table 10-1

Schedule of Visits

Procedure/Assessment	Visit 0 (-42 to -1 days) Screening	Visit 00 (Day 0) Surgery	Visit 1 (+1 day) 1 Day Follow-up	Visit 2 (+5 to 9 days) 1 Week Follow-up	Visit 3 (+21 to 35 days) 1 Month Follow-up	Visit 4 (+70 to 98 days) 3 Month Follow-up	Visit 5 (+150 to 210 days) 6 Month Follow-up	Visit 6 (+330 to 420 days) 12 Month Follow-up	Visit 7 (+690 to 780 days) 24 Month Follow-up	Visit 8 (+1050 to 1140 days) 36 Month Follow-up/Exit/Early Exit
Informed Consent	X									
Demographics	X									
Medical History	X	X	X	X	X	X	X	X	X	X
Concomitant Medications	X	X	X	X	X	X	X	X	X	X
Number of Ocular Hypotensive Medications	X ¹	X	X	X	X	X	X	X	X	X
Urine Pregnancy Test ²	X									
Inclusion/Exclusion	X									
Surgery ³ (with video)		X								
Manifest Refraction	X ¹			X	X	X	X	X	X	X
Monocular BCDVA	X ^{1,4}		X ⁵	X	X	X	X	X	X	X
Specular Microscopy ⁶	X ¹					X	X	X	X	X
Visual Field ⁷	X ¹							X	X	X
IOP (8:00 – 10:00 am)	X ¹		X	X	X	X	X	X	X	X
Slit Lamp Examination	X ¹		X	X	X	X	X	X	X	X
Gonioscopy (photographed)	X ¹	X	X	X	X	X	X	X	X	X
Fundus Examination	X ¹					X	X	X	X	X
Central Corneal Pachymetry	X ¹							X	X	X
UBM or OCT ⁸						(X)	(X)	(X)	(X)	(X)
Adverse Events	X	X	X	X	X	X	X	X	X	X
Device Deficiencies	X	X	X	X	X	X	X	X	X	X

¹ Conduct bilaterally at Visit 0 and in study eye only at postoperative visits, unless otherwise indicated.

² In women of child bearing potential only.

³ An Alcon observer may be present during surgery.

⁴ At Visit 0, if BCDVA better than 0.3 logMAR (> 85 letters read), repeat with BAT (Brightness Acuity Meter).

[figure not shown]
⁵ At Visit 1 (Day 1 Follow-up) BCDVA will be conducted as a pinhole test.

⁶ ECD may be requested in the fellow eye at follow-up on a case by case basis.

⁷ Visual field testing may be repeated between screening (Visit 0) and surgery (Visit 00), if needed.

⁸ UBM or OCT conducted if CyPass is not visible on Gonioscopy at two consecutive visits after Visit 3 (1 Month Follow-up). Images retained at site to demonstrate placement of CyPass.

11 Appendix B: Study Design

12 Appendix C: Data Sources

Endpoint	CRF	Comments
Primary Effectiveness Endpoint		
None		
Secondary Effectiveness Endpoints		
Mean change in IOP	Baseline: Intraocular Pressure_Glaucoma PostOp: Intraocular Pressure_Glaucoma_1	
Proportion of subjects with IOP reduction \geq 20% while using the same or fewer topical ocular hypotensive medications	Baseline: Intraocular Pressure_Glaucoma PostOp: Intraocular Pressure_Glaucoma_1 Ocular Hypotensive Medications	
Proportion of subjects who are not using ocular hypotensive medication with IOP \geq 6 mmHg and \leq 18 mmHg	Baseline: Intraocular Pressure_Glaucoma PostOp: Intraocular Pressure_Glaucoma_1 Ocular Hypotensive Medications	
Primary Safety Endpoint		
Failure to implant CyPass, defined as inability to successfully deploy or insert the CyPass.	Adverse Event(s) SX	Intraop - g) CyPass non-implantation (as defined in the protocol)

Endpoint	CRF	Comments
Clinically significant CyPass malposition, defined as CyPass positioning after deployment such that:		
The device is not in the supraciliary space, or	Adverse Event(s) SX	Postop - bb) CyPass device malposition - positioning after deployment such that the device is not in the supraciliary space (Specify)

Endpoint	CRF	Comments

There is a clinical sequela resulting from device position including, but not limited to:
 
Secondary surgical intervention to modify device position (eg, repositioning, proximal end trimming or explantation)
 
Corneal endothelial touch by device
 
Corneal edema leading to loss of BCDVA > 2 lines at the last postoperative visit, in comparison with preoperative BCDVA
 
Progressive ECL, defined as ongoing reduction in endothelial cell count of 30% or more relative to the screening ECD value, where 'ongoing reduction in endothelial cell count' is defined as losses continuing after Visit 5 (6 Month Follow-up)
 
Erosion of device through sclera
 
Device obstruction requiring secondary surgical intervention.
		Postop - cc) CyPass device malposition - positioning after deployment such that there is a clinical sequela resulting from device position (as defined in the protocol) (Specify)
Secondary Safety Endpoints		
Rate of occurrence of sight-threatening adverse events including		

Endpoint	CRF	Comments
Persistent (at time of study exit) BCDVA loss of 3 or more lines compared to best BCDVA achieved during the course of study	Adverse Event(s) SX	Postop - b) Persistent BCDVA loss of 3 lines or more (as defined in the protocol)
Endophthalmitis	Adverse Event(s) SX	Postop - d) Endophthalmitis
Corneal decompensation	Adverse Event(s) SX	Postop - n) Corneal decompensation
Retinal detachment	Adverse Event(s) SX	Postop - p) Retinal detachment
Severe choroidal hemorrhage or detachment	Adverse Event(s) SX	Postop - t) Choroidal hemorrhage or choroidal effusion (as defined in the protocol) lasting longer than 1 month (Specify)
Aqueous misdirection	Adverse Event(s) SX	Postop - h) Aqueous misdirection
The rate of ocular secondary surgical interventions (SSI)	Adverse Event(s) SX	
Any one of these four:
 
Postop - ee) CyPass device explantation associated with CyPass placement and stability
 
Postop - ff) CyPass device explantation NOT associated with CyPass placement and stability
 
Postop - gg) Unplanned ocular surgical reintervention associated with CyPass placement and stability
 
Postop - hh) Unplanned ocular surgical reintervention NOT associated with CyPass placement and stability (as defined in the protocol)

Endpoint	CRF	Comments
The rate of ocular SSIs associated with CyPass placement and stability	Adverse Event(s) SX	
Either of these two:
 
Postop - ee) CyPass device explantation associated with CyPass placement and stability
 
Postop - gg) Unplanned ocular surgical reintervention associated with CyPass placement and stability

Other Safety Endpoints		
Increase from baseline IOP of 10 mmHg or greater at any time at/after 30 days postoperative	Baseline: Intraocular Pressure_Glaucoma PostOp: Intraocular Pressure_Glaucoma_1	
BCDVA loss of 2 or more lines compared to screening (Visit 0)	Baseline: Visual Acuity_VAS PostOp: Visual Acuity_VAS_1	
BCDVA loss of 2 or more lines in comparison with best recorded BCDVA at any postoperative visit	Baseline: Visual Acuity_VAS PostOp: Visual Acuity_VAS_1	

Endpoint	CRF	Comments
Device movement, defined as a change by at least 1 in the number of CyPass rings visible (eg, from 1 ring to 2 rings or from 3 rings to 2 rings) that does not result in clinical sequelae (eg, secondary surgical intervention to modify device position, corneal endothelial touch by device, corneal edema leading to loss of BCDVA > 2 lines at the last postoperative visit in comparison with preoperative BCDVA, progressive endothelial cell loss, erosion of device through sclera, or device obstruction requiring secondary surgical intervention), and that is not attributable to any one or more of the following:	Adverse Event(s) SX	Postop - dd) CyPass device dislodgement or movement, without sequelae (as defined in the protocol)
variations in gonioscopic viewing angle or illumination		
changes in angle anatomy due to concomitant findings such as resolution of hyphema		
changes in anterior chamber depth		
development of focal peripheral anterior synechiae		

Endpoint	CRF	Comments
Additional Safety Assessments		
Adverse events (ocular and non-ocular)	Adverse Event(s) SX	
Device deficiencies	Device Deficiency	
Endothelial Cell Count	This will come from a dataset provided by the reading center, CIARC	
Slit lamp findings	Baseline: Slit Lamp Observations PostOp: Slit Lamp Observations_1	
Fundus examination (C/D ratio) and fundus findings	Baseline C/D: Fundus Exam PostOp C/D: Fundus Exam_1 Baseline observations: Fundus Observations PostOp observations: Fundus Observations_1	
Corneal pachymetry	Baseline: Corneal Thickness PostOp: Corneal Thickness_1	
Intraocular pressure	Baseline: Intraocular Pressure_Glaucoma PostOp: Intraocular Pressure_Glaucoma_1	
Visual field loss mean deviation testing	Baseline: Automated Perimetry PostOp: Automated Perimetry_1	
Manifest refraction	Baseline: Subjective Refraction PostOp: Subjective Refraction_1	
Monocular BCDVA	Baseline: Visual Acuity_VAS PostOp: Visual Acuity_VAS_1	
Gonioscopy (with Goniophotography) via UBM or OCT	Baseline: Gonioscopy PostOp: Gonioscopy_1	
Secondary Surgical Interventions	Adverse Event(s) SX	
CyPass Explantation and/or Repositioning	Adverse Event(s) SX	

13 Appendix D: Cylinder Adjustment Converting Negative to Positive Notation

Transform cylinder to positive notation (+ notation) using the following:

When CYLINDER_RAW is negative but not missing:

- ≠ Positive notation for sphere: SPHERE_RAW + CYLINDER_RAW
- ≠ Positive notation for cylinder: multiply CYLINDER_RAW by negative one
- ≠ Positive notation for refractive axis: AXIS + 90, if this is greater than 180, then subtract 180 from it.

Otherwise:

- ≠ Use current values of CYLINDER_RAW and SPHERE_RAW, and positive notation for REFRAK is the value of AXIS

Data that is converted to positive notation will have the same level of precision as the original data collected in the database.

14 Appendix E: Conversion of Visual Acuity Score to Snellen Values

LogMar	VAS	Snellen
2.00	0	20/2000
1.98	1	
1.96	2	
1.94	3	
1.92	4	
1.90	5	20/1600
1.80	10	20/1250
1.70	15	20/1000
1.60	20	20/800
1.50	25	20/630
1.40	30	20/500
1.30	35	20/400
1.20	40	20/320
1.10	45	20/250
1.00	50	20/200
0.98	51	
0.96	52	
0.94	53	
0.92	54	

LogMar	VAS	Snellen
0.90	55	20/160
0.88	56	
0.86	57	
0.84	58	
0.82	59	
0.80	60	20/125
0.78	61	
0.76	62	
0.74	63	
0.72	64	
0.70	65	20/100
0.68	66	
0.66	67	
0.64	68	
0.62	69	
0.60	70	20/80
0.58	71	
0.56	72	
0.54	73	
0.52	74	
0.50	75	20/63
0.48	76	
0.46	77	
0.44	78	
0.42	79	
0.40	80	20/50
0.38	81	
0.36	82	
0.34	83	
0.32	84	
0.30	85	20/40
0.28	86	
0.26	87	
0.24	88	
0.22	89	
0.20	90	20/32
0.18	91	
0.16	92	
0.14	93	
0.12	94	
0.10	95	20/25
0.08	96	
0.06	97	
0.04	98	

LogMar	VAS	Snellen
0.02	99	
0.00	100	20/20
-0.02	101	
-0.04	102	
-0.06	103	
-0.08	104	
-0.10	105	20/16
-0.12	106	
-0.14	107	
-0.16	108	
-0.18	109	
-0.20	110	20/12.5
-0.22	111	
-0.24	112	
-0.26	113	
-0.28	114	
-0.30	115	20/10
